#### 4.2.2 Variables used for Stratification at Randomisation

The randomisation will be stratified by baseline Hurley Stage (II versus III) and anatomical location of the surgical site (i.e., axilla versus inguinal region).

### 4.3 Endpoint

#### 4.3.1 Primary Efficacy Endpoint

The primary efficacy variable is the proportion of subjects achieving HiSCR at Week 12. HiSCR is defined as at least a 50% reduction in the AN count with no increase in abscess count and no increase in draining fistula count relative to baseline.

### 4.3.2 Secondary Efficacy Endpoints

[figure not shown]
#### Ranked Secondary Efficacy Variables

- 1. Proportion of subjects achieving HiSCR-es (defined as the HiSCR excluding the HS surgical site) at Week 12
- 2. Proportion of subjects achieving HiSCR-es at Week 24
- 3. Percent change in surface area of the HS surgical site from Baseline to Week 12
- 4. Proportion of subjects at Week 12 that require a less extensive surgery than the surgical plan (determined at Baseline) or no surgery as determined by the designated surgeon

### 4.3.3 Other Efficacy Endpoints

Other efficacy variables to be analysed at each scheduled visit in Periods A and C, except for the ones included as the primary or ranked secondary variables that will be analysed for visits other than Weeks 12 and 24 include:

- Change from Baseline in CRP
- Proportion of subjects with DLQI = 0
- Proportion of subjects with DLQI = 0 or 1
- Change from Baseline in DLQI score
- Change from Baseline in EQ-5D index
- Change from Baseline in HS-PGA-SP

- Change from Baseline in HSIA
- Change from Baseline in HSSA-7d
- Change from Baseline in SF-12
- Change from Baseline in TSQM
- Change from Baseline in WPAI:SHP
- Proportion of subjects that experience a flare, defined as an at least 25% increase in AN count with a minimum increase of 2 relative to Baseline at each study visit, during Period A and during the study
- Proportion of subjects that experience at least 25% increase in each lesion type with a minimum increase of 2 relative to Baseline at each study visit, during Period A and during the study

For the proportion of subjects that experience a flare, and that experience at least 25% increase in each lesion type with a minimum increase of 2 relative to Baseline, analyses will be performed across all body regions at visits during Period A, and across body regions excluding the HS surgical site at all visits during the study.

Of note, HS PGIC is assessed for the validation of HS-PGA-SP for skin pain only and will not be analysed for efficacy.

### 4.3.4 Safety Endpoint

[figure not shown]
Adverse events, laboratory data, physical examinations, and vital signs will be collected, monitored, assessed, and recorded at the designated study visits listed in study protocol Appendix C and as described in study protocol Section 6.0 and Table 1.

### 4.3.5 Pharmacokinetic Endpoint

The pharmacokinetic endpoints will be analysed separately.

### 4.4 Sample Size Justification

The study is designed to enroll approximately 200 subjects. Assuming the true treatment difference in this study population is at least 20%, 100 subjects per arm will provide at

least 80% power to detect the treatment difference at the alpha level of 0.05. The study also has at least 80% power to demonstrate the point estimate of the treatment difference of at least 15%.

The response rates observed in the combined PIONEER I and II studies (Studies M11-313 and M11-810, respectively) for the HiSCR at Week 12 were 50.6% and 26.8% in the adalimumab ew group and placebo group, respectively. Due to the potential differences between the population of moderate-to-severe HS patients who are surgical candidates and the general moderate-to-severe HS patient population, a conservative estimate of 20% treatment difference is used for the power calculation.

#### 4.5 Interim Analysis

No interim analysis is planned in this study.

[figure not shown]
### 4.6 Multiplicity Testing Procedures for Type-I Error Control

The statistical comparisons for the primary efficacy variable and the ranked secondary variables will be carried out in the hierarchical order under a two-sided significance level of 0.05.

### 4.7 Missing Data Imputation

Missing data will be imputed using the following methods for the efficacy analyses in the ITT Population defined in Section 5.0 below:

- Non-Responder Imputation (NRI): the NRI analysis will categorize any subject who has a missing value at a specific visit as non-responder for that visit. The only exception is when if the subject is a responder both before and after a specific visit window, then the subject will be categorized as a responder for the visit. The NRI will be the primary approach in the analyses of categorical variables. For analyses up to Week 12, NRI will be applied using evaluations within the period.
- Last Observation Carried Forward (LOCF): The LOCF analyses will use the completed evaluation from the previous visit within the particular period for

[figure not shown]
efficacy measures assessed to impute missing data at later visits in the same period. Baseline efficacy evaluations will not be carried forward. LOCF will be the primary approach in the analyses of continuous variables, and the secondary approach in the analyses of categorical variables.

 As-Observed: The As-observed analyses will not impute values for missing evaluations, and thus a subject who did not have an evaluation on a scheduled visit will be excluded from the As-observed analysis for that visit. Asobserved analyses will be the secondary approach in the analyses of continuous variables.

Multiple Imputation (MI) for missing values will be performed for the primary efficacy variable. MI analysis will be carried out in three steps:

- Imputation of missing data. The imputation will be generated for each type of lesion count (abscess, inflammatory nodule, and draining fistula) as HiSCR components. The variables to be included in the imputation model are: Baseline lesion count for the corresponding type, smoking status, treatment group, stratification factors, and lesion count for the corresponding type at each visit from randomisation up to the end of the analysis period. For each component, 20 'complete' datasets will be generated from monotone regression model at each visit using SAS PROC MI. The seed for PROC MI will be set as the numeric form of the date when the first subject from this study is randomised. The imputed post-baseline lesion counts will be rounded to integers before the determination of HiSCR status. Subjects who discontinued due to lack of efficacy will be forced as non-responders.
- Analysis of imputed data sets. A Cochran-Mantel-Haenszel (CMH) test using Wilson-Hilferty transformation, stratified by stratification factors, will be used to analyse HiSCR response rates in each imputed dataset.
- Synthesis of imputation and analysis results. SAS PROC MIANALYZE will be used to generate the final inferences of the risk difference between treatment groups.

The 3rd and 4th ranked secondary endpoints will only be analysed by OC approach. For subjects whose surgery is no longer needed due to HS improvement, the actual surgical

area would be treated as 0 and the type of surgery would be treated as a less-extensive surgery. Subjects who discontinued before surgery due to AE of worsening in HS, or exceeding protocol specified number of lesion interventions, or planned HS surgery performed prior to Week 13, will be forced as no change in the planned surgical area and no less-extensive surgery.

In all methods of handling missing data, efficacy assessments observed on or before the planned surgery cannot be used to impute missing values for post-surgery visits, except for the lesion count on body regions other than the surgical site.

[figure not shown]
Lesions that receive protocol-allowed intervention (e.g., contained within the excised surgical specimen, protocol-allowed minor interventions including incision and drainage) will be counted as permanently present from the date of the intervention.

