### 6.0 Efficacy Analysis

#### 6.1 General Considerations

[figure not shown]
The efficacy analysis will be conducted among the ITT Population. A sensitivity analysis for the primary efficacy endpoint may also be conducted among the Per-protocol Population, if defined.

Categorical variables will be analysed using Cochran-Mantel-Haenszel (CMH) test, stratified by baseline Hurley Stage and anatomical location of the surgical. Continuous variables will be analysed using ANCOVA method, with treatment, baseline Hurley Stage, anatomical location of the surgical, and Baseline values in the model.

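### Does the multiple-imputation sensitivity analysis in SAP 4.7 need a named risk-difference estimator, joint imputation of lesion types, and the body-weight model written in?

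*SAP*

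**What the plan says.** Protocol 8.1.4.1 makes non-responder imputation (NRI) the primary approach for HiSCR at Week 12, with LOCF and multiple imputation (MI) as sensitivity analyses. It defines the difference as adalimumab minus placebo and asks for a 95% confidence interval.

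SAP 4.7 sets out the MI in three steps.

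- **Imputation.** "The imputation will be generated for each type of lesion count (abscess, inflammatory nodule, and draining fistula) as HiSCR components". Apart from smoking status, treatment and strata, the predictors are that type's own baseline value and the "lesion count for the corresponding type at each visit from randomisation up to the end of the analysis period". Twenty "datasets will be generated from monotone regression model at each visit using SAS PROC MI". Then "The imputed post-baseline lesion counts will be rounded to integers before the determination of HiSCR status", and "Subjects who discontinued due to lack of efficacy will be forced as non-responders".
- **Analysis.** A CMH "test using Wilson-Hilferty transformation, stratified by stratification factors, will be used to analyse HiSCR response rates in each imputed dataset".
- **Pooling.** "SAS PROC MIANALYZE will be used to generate the final inferences of the risk difference between treatment groups".

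SAP 6.1 repeats the CMH "test, stratified by baseline Hurley Stage and anatomical location of the surgical" site. SAP 3.0 describes the document as high-level and leaves programming conventions to a supplement, which is not among the documents reviewed.

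Protocol 8.1.4.1 also calls for a logistic sensitivity analysis of the primary endpoint controlling for change in body weight, with its details to be given in the SAP. SAP version 3.0 (12 August 2019) uses weight only as a subgroup split at the median (SAP 6.5).

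**The concern.** Three things look wrong on a first reading.

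1. **Pooling.** MIANALYZE combines an estimate and a standard error from each dataset. The stated second step delivers a test statistic that has neither, nor a sign. The promised output cannot be built from the stated input, and no section names the stratified estimator or its variance.
2. **Imputation model.** HiSCR requires a fall in the sum of two lesion types and no rise in abscesses or draining fistulas. Imputing each type from its own history discards any dependence between types, and rounded linear regression suits skewed counts poorly. MI response rates could be too low.
3. **Weight model.** An analysis promised in the protocol is missing from the document meant to specify it, and no rule is set for a missing weight in that model.

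At stake would be the credibility of the sensitivity analyses, with estimator and covariates left open to choice after unblinding.

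**Working it through.** **The plan's own figure.** The MI section states no number. The nearest is the power in Protocol 8.2: at least 80% with 100 per arm, a 20-point difference and two-sided alpha 0.05. Taking placebo at the quoted 26.8% and adalimumab at 46.8%, the average rate is 0.368 and

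z = [0.20 × √100 − 1.96 × √(2 × 0.368 × 0.632)] / √(0.468 × 0.532 + 0.268 × 0.732) = (2 − 1.337) / 0.667 = 0.99,

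which gives power of 84.0%. The statement reproduces, and nothing in the MI section affects it.

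**Pooling: is the gap real?** Let Q be the CMH statistic. With 1 degree of freedom, the Wilson-Hilferty transform is W = (Q^(1/3) − 7/9) / √(2/9). Hypothetical results with 100 per arm, treated as a single stratum:

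| Responders (adalimumab v placebo) | Q | W | Difference (SE), points |
|---|---|---|---|
| 47 v 27 | 8.54 | 2.69 | +20.0 (6.7) |
| 27 v 47 | 8.54 | 2.69 | −20.0 (6.7) |
| 23 v 8 | 8.55 | 2.69 | +15.0 (5.0) |

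For the first row, Q = (47 − 37)² / [100 × 100 × 74 × 126 / (200² × 199)] = 100 / 11.71 = 8.54. One W fits three different effects, so an estimator must be supplied.

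**Pooling: does the choice matter?** Take invented data in four strata: adalimumab 18/30, 12/26, 10/24, 7/20 and placebo 12/30, 7/25, 5/25, 3/20. The Mantel-Haenszel weights n₁n₀/N are 15.00, 12.75, 12.24 and 10.00. The weighted difference is 9.967 / 49.99 = 0.199, with Q = 8.69 and W = 2.71. Candidate standard errors are:

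- Sato or stratified binomial: 0.0655
- crude unpooled: 0.0668
- back-calculated from the test, 0.1994 / √8.69: 0.0676

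The lower 95% limit runs from 0.1994 − 1.96 × 0.0676 = 0.067 to 0.1994 − 1.96 × 0.0655 = 0.071, a spread of 0.4 points.

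**Imputation model.** The documents give no dropout rate, lesion distribution or correlation between types, so all inputs here are assumptions. The simulation used 100 per arm and true HiSCR of 26.8% v 46.8%. It crossed nine lesion settings (cross-type correlation 0, 0.5 or 0.9; few or many lesions; mild to strong skew; high persistence) with six missingness patterns (5 to 15% missing), giving 54 combinations of 400 trials with 20 imputations each.

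| Method | Error in treatment difference, points |
|---|---|
| SAP method | −0.9 to +0.1 |
| Joint predictive mean matching | −0.8 to 0.0 |
| LOCF | −1.4 to −0.2 |
| NRI | −3.1 to −0.3 |

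The largest SAP error is 0.9 / 6.7 = 0.13 of a standard error. The arm rates do suffer: among imputed subjects the SAP method keeps 56 to 84% of true response. Joint matching keeps 87 to 104% in 45 combinations but 108 to 137% in the nine where dropout depends strongly on worsening.

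An independent calculation with assumed true rates near 28% and 46 to 48% agrees. At correlation 0.6 with 10% missing, separate imputation gives imputed-subject rates of 32.2% and 17.2%, and joint imputation 39.1% and 24.5%. The overall differences are 18.99 and 18.95 points. Across all its settings the two methods differed by less than 0.3 points.

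**Weight model.** The protocol supplies the endpoint, model type and covariate. If 5 to 15% of weights were missing (an assumption), 0.05 × 200 to 0.15 × 200, or 10 to 30 subjects, would drop out of this one model.

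**The case for a change.** The best case for a change is that the SAP fixes the seed, the rounding and the number of imputations, so it could as easily name the estimator. There is also one place where silence could mislead. W is an upper-tail transform: at Q = 3.84, W is 1.67 and its upper tail is 0.047, but reading a pooled W two-sidedly gives about 0.095. That is fair, and the reading should be from the upper tail, because the chi-square test is already two-sided. But no decision uses this P value. The testing rules in SAP 4.6, 6.2 and 6.3 do not refer to the MI result, and the 15% point estimate in SAP 4.4 is a power statement that no testing rule uses.

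On imputation, the loss in arm-level response is real under the assumed distributions. It is not due to separate imputation alone. In one illustrative setting with zero correlation between types, true adalimumab response was 35.0%, separate linear imputation gave 24.6% and joint linear imputation 24.4%, so the loss there came from fitting a linear model to skewed counts. At correlation 0.9 joint modelling did help (46.5% true, 29.5% separate, 36.3% joint). Which case applies is unknown.

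On weight, the protocol names the SAP as the place for the detail, its amendment summary says regulatory authorities asked for the analysis, and a supplement does not strictly meet that wording. As a documentary omission this stands. SAP 7.1 leaves missing safety data unimputed and Protocol 5.3.1.1 lists weight under vital signs, so a missing-weight convention arguably exists, though subjects would still be lost from the model.

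**Conclusion.** The observations are accurate, but they do not call for a change to the plan.

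- **Pooling** is a gap that an analyst fills sensibly. The protocol fixes the direction, SAP 4.7 the scale and SAP 6.1 the strata. A stratified Mantel-Haenszel difference with a standard variance is the natural reading, and reasonable variants differ by about 0.4 points at the confidence limit in the illustrative data.
- **Separate imputation** is a fair trade-off. SAP 4.7 promises a risk difference from MI, and on that quantity joint predictive mean matching gains almost nothing while overstating response when dropout follows strong worsening. Arm-level MI rates are best read as likely to be low, subject to lesion distributions and dropout that the documents do not give.
- **The weight analysis** is missing detail for a supportive model. The protocol's commitment to run it stands whether or not the SAP repeats it. Treatment and the stratification factors are the obvious companions to weight change. Because that covariate is measured after randomisation, the result could not override the randomised comparison.

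The primary NRI analysis, the LOCF analysis, the hierarchy and the sample size are unaffected on any of these counts.

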A total of two protocol-allowed interventions are permissible during Period A. An intervention can occur on maximally two different lesions at the same visit or on the same lesion at two different study visits. The same lesion cannot be treated two times at the same visit. If a subject requires more than two interventions within the first 12 weeks, then the subject must be discontinued from the study.

During Period B (including during the excisional surgery) protocol-allowed interventions (i.e., intra-lesional injection, incision and drainage) are not permitted.

During Period C, maximally two interventions every 4 weeks are permitted. An intervention can occur on two different lesions at the same visit or on the same lesion at two different study visits. Within each 4-week period, the same type of intervention cannot be used two times on the same lesion. If a subject requires more than two interventions within a 4-week period or has two of the same interventions on the same lesion within that same 4-week period, then a protocol deviation must be recorded in the source and on the appropriate eCRF.

All study visit evaluations must occur before any interventions are performed. Any lesion that undergoes an intervention will be documented in the source. The Study Investigator will be required to count any lesion that undergoes an intervention as permanently present from the date of the intervention, and must record this in the source and on the appropriate eCRF.

Study Drug

Study drug administration will be documented in a separate section of the eCRF. All study visit evaluations must occur before the study drug is administered.

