5.2.3.4 Rescue Therapy

If the Study Investigator, with agreement of the designated surgeon, determines the subject must undergo excision of the HS surgical site prior to the Week 13 study visit window (i.e., more than 7 days prior to the scheduled Week 13 study visit) all study

procedures scheduled for Week 12 must be performed and recorded, and the subject must be discontinued from the study.

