8.1.4 Statistical Analyses of Efficacy

The efficacy analysis will be conducted in the ITT Population and PP Population, if defined.

Visit windows and the data handling convention for summarizing efficacy results will be defined in the SAP.

Missing data will be imputed using the following methods for the efficacy analyses in the ITT Population:

- **Non-Responder Imputation (NRI):** the NRI analysis will categorize any subject who has a missing value at a specific visit as non-responder for that visit. The NRI will be the primary approach in the analyses of categorical variables. For analyses up to Week 12, NRI will be applied using evaluations within the period.
- **Last Observation Carried Forward (LOCF):** The LOCF analyses will use the completed evaluation from the previous visit within the particular period for efficacy measures assessed to impute missing data at later visits in the same period. Baseline efficacy evaluations will not be carried forward. LOCF will be the primary approach in the analyses of continuous variables, and the secondary approach in the analyses of categorical variables.
- **As-Observed:** The As-observed analyses will not impute values for missing evaluations, and thus a subject who did not have an evaluation on a scheduled visit will be excluded from the As-observed analysis for that visit. As-observed analyses will be the secondary approach in the analyses of continuous variables.

Multiple Imputation (MI) for missing values will be performed for the primary efficacy variable.

Lesions that receive intervention (e.g., contained within the excised surgical specimen, protocol-allowed minor interventions including incision and drainage) will be counted as permanently present from the date of the intervention.

In order to evaluate the impact of major protocol violations on the results of the trial, efficacy assessments obtained after the start of a major protocol-disallowed treatment will be excluded from the analysis. Subjects will be counted as non-responders for the categorical variable from the date of the major protocol-disallowed treatment and have their LOCF for continuous variables. The exclusion of efficacy assessments will be determined via classification prior to the database lock.

Additional analyses may be performed for the primary efficacy variable adjusting for baseline covariates in addition to the stratification factors.

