### 6.3 Secondary Efficacy Analysis

The following null hypotheses for ranked secondary endpoints below will be tested in a hierarchical order using two-sided significance level of 0.05 only if the null hypothesis for the primary endpoint has been rejected:

- 1. Adalimumab is not different from placebo with respect to the proportion of subjects achieving HiSCR-es at Week 12
- 2. Adalimumab is not different from placebo with respect to the proportion of subjects achieving HiSCR-es at Week 24
- 3. Adalimumab is not different from placebo with respect to the percent change in surface area of the HS surgical site from Baseline to Week 12
- 4. Adalimumab is not different from placebo with respect to the proportion of subjects at Week 12 that require a less extensive surgery than the surgical plan (determined at Baseline) or no surgery as determined by the designated surgeon

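### Ranked endpoint 4 is analysed on observed cases only, lack of efficacy is missing from the forced-failure rule for endpoints 3 and 4, and no sensitivity analysis covers the subjects left out

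*SAP*

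**What the plan says.** Endpoint 4 is defined in SAP 4.3.2 as "Proportion of subjects at Week 12 that require a less extensive surgery than the surgical plan (determined at Baseline) or no surgery", as judged by the designated surgeon. SAP 6.3 tests it last, in "hierarchical order using two-sided significance level of 0.05 only if the null hypothesis for the primary endpoint has been rejected".

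The general missing-data rule for binary endpoints is in Protocol 8.1.4: "The NRI will be the primary approach in the analyses of categorical variables". SAP 4.7 repeats it. For ranked endpoints 3 (percent change in area) and 4, however, SAP 4.7 says that these "ranked secondary endpoints will only be analysed by OC approach". OC is not spelled out; I read it as the as-observed method of the same section, which excludes a subject without the evaluation.

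SAP 4.7 then adds two assignment rules for these endpoints:

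- A subject who no longer needs the operation because HS improved gets area 0 and counts as a success on endpoint 4.
- Three kinds of leaver are set to unchanged area and to failure on endpoint 4. The list begins "Subjects who discontinued before surgery due to AE of worsening in HS, or exceeding protocol specified number of lesion interventions" and ends with planned surgery done before Week 13.

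The protocol itself requires two of those three exits. Section 5.2.3.2: "If a subject requires more than two interventions within the first 12 weeks, then the subject must be discontinued from the study". Section 5.2.3.4, for early excision: all "procedures scheduled for Week 12 must be performed and recorded, and the subject must be discontinued from the study".

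Lack of efficacy is not on the list. Yet in the multiple imputation for HiSCR, SAP 4.7 says: "Subjects who discontinued due to lack of efficacy will be forced as non-responders".

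**The concern.** Three things do not fit together.

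1. A binary endpoint in the confirmatory hierarchy is taken out of the documents' NRI rule, and no reason is given.
2. The SAP accepts that HS-related exits before surgery are failures, but leaves out the one reason that it names elsewhere as treatment failure. The same subject could be a forced non-responder in the HiSCR multiple imputation and absent from endpoints 3 and 4.
3. The word *only* shuts out any second analysis. Multiple imputation covers the primary variable alone, the optional per-protocol analysis covers the primary endpoint alone, and SAP 6.3 adds nothing.

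At stake is the claim that adalimumab reduces the surgery needed. It would rest on a single analysis whose denominator depends on how many subjects in each arm leave for unlisted reasons, some of them treatment failures. Endpoint 4 is last, so its own handling affects no later test, but endpoint 3 gates it.

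**Working it through.** **Inputs.** From the documents: 100 per arm, 1:1 allocation, two-sided 0.05 (Protocol 8.2, SAP 4.4 and 6.3). The documents give no success rate, effect, power or dropout by reason for endpoint 4, so there is no plan figure to reproduce here. All counts below are assumed. Arms are in the order adalimumab vs placebo.

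**Formula for A and B.** Pearson chi-square without continuity correction, an unstratified stand-in for the planned CMH test: d = x₁/n₁ − x₂/n₂; p̄ = (x₁+x₂)/(n₁+n₂); χ² = d² / [p̄(1−p̄)(1/n₁+1/n₂)], 1 df.

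**A. Lack-of-efficacy leavers only.** Five other unlisted leavers per arm are excluded throughout. The denominator as written is 95 minus the lack-of-efficacy leavers; with those leavers scored as failures it is 95.

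Worked case, 23 vs 12 successes and 2 vs 8 leavers:

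- As written: d = 23/93 − 12/87 = 0.2473 − 0.1379 = 0.1094; p̄ = 35/180 = 0.1944; χ² = 3.43, p = 0.064.
- Scored as failures: d = 23/95 − 12/95 = 0.2421 − 0.1263 = 0.1158; p̄ = 35/190 = 0.1842; χ² = 4.24, p = 0.040.

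| Successes | Lack-of-efficacy leavers | As written | Scored as failures |
|---|---|---|---|
| 23 vs 12 | 2 vs 8 | 10.9 points, p = 0.064 | 11.6 points, p = 0.040 |
| 22 vs 12 | 8 vs 2 | 12.4 points, p = 0.034 | 10.5 points, p = 0.058 |
| 23 vs 12 | 5 vs 5 | p = 0.038 | p = 0.040 |
| 26 vs 12 | 2 vs 8 | p = 0.020 | p = 0.011 |
| 26 vs 12 | 8 vs 2 | p = 0.005 | p = 0.011 |

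**B. All unlisted leavers.** Observed cases (OC) removes them; NRI keeps 100 per arm.

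| Successes | Unlisted leavers | OC | NRI |
|---|---|---|---|
| 22 vs 12 | 15 vs 5 | 22/85 vs 12/95, p = 0.023 | p = 0.060 |
| 24 vs 12 | 5 vs 15 | 24/95 vs 12/85, p = 0.062 | p = 0.027 |
| 26 vs 12 | 15 vs 5 | 26/85 vs 12/95, p = 0.003 | p = 0.012 |
| 26 vs 12 | 5 vs 15 | 26/95 vs 12/85, p = 0.030 | p = 0.012 |

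**C. Rejection rate with no true difference.** Simulated stratified CMH test: 4 strata of 25 per arm, 30% success in both arms, 40,000 runs per setting. Two-sided rejection, OC / NRI:

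| Who leaves | 10% vs 10% | 15% vs 5% | 5% vs 15% |
|---|---|---|---|
| Failures only | 5.3% / 5.3% | 8.0% / 4.9% | 8.3% / 5.0% |
| Unrelated to outcome | 5.1% / 5.1% | 4.9% / 7.5% | 5.1% / 7.6% |
| Half and half | 5.1% / 5.1% | 5.9% / 5.7% | 5.9% / 5.7% |

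Each method fails where the other holds. With equal dropout both stay at about 5%.

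**The case against.** **The restriction has a visible source.** Protocol 8.1.1 and SAP 5.1 limit surgery-related endpoints in Periods B and C to operated subjects, and the actual area is measured at surgery. This may be what the authors had in mind. It cannot govern endpoint 4, which is a Week 12 endpoint, counts having no operation as success, and falls under Protocol 8.1.4.2, which places the secondary analyses in the ITT population. SAP 4.7 itself assigns values to unoperated subjects. The lack of interim surgical assessments could explain dropping LOCF, but not NRI.

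**The rule is specific and pre-specified.** True: SAP version 3 states that its changes precede database lock and unblinding. That answers a charge of data-driven choice, not the inconsistency.

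**The gap is narrow.** Protocol 6.1.1.1 makes worsening of an existing condition an adverse event, so many treatment failures can enter through the first listed reason, and Protocol 5.4.1 does not name lack of efficacy as a withdrawal criterion. What remains is a subject who did not worsen, is recorded under lack of efficacy alone, and has no surgical evaluation. The documents do not show how common this is. But failing to improve is not worsening, and SAP 4.7 treats lack of efficacy as a category of its own.

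**The examples sit on the threshold.** This stands. In A, with 12 placebo successes, only one adalimumab count between 12 and 60 changes the verdict for 2 vs 8 leavers (23) and only one for 8 vs 2 (22); for 4 vs 6 none does. The estimate moves by 0.7 points (11.6 − 10.9) or 1.9 points (12.4 − 10.5). If these leavers are mainly on placebo, the written rule works against adalimumab.

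**NRI is no better in general.** This also stands, as C shows. It argues against making NRI primary on these grounds. It also argues against relying on one method alone.

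**The supplement may cover it.** SAP 3.0 defers details to a supplement that was not available. An extra analysis placed there would contradict the word *only*.

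**Conclusion.** The concern holds. The SAP departs without explanation from the NRI rule for a binary endpoint in the hierarchy, omits lack of efficacy from a list that already scores comparable exits as failures, and provides no sensitivity analysis for endpoints 3 or 4.

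The practical size is modest. It is negligible if unlisted dropout is balanced, can go either way if not, and alters the conclusion only for results close to 0.05. In the most unfavourable simulated settings, a 10-point imbalance in dropout raises the two-sided error to about 8%. These sizes rest wholly on assumed counts. For endpoint 3 the inconsistency is in the text and its effect was not quantified. The change is worth making because it is cheap and is credible only if made before unblinding; it is not a fatal flaw.

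**What to change.** 1. In SAP 4.7, add discontinuation before surgery for lack of efficacy to the list of exits scored as unchanged area and failure, for endpoints 3 and 4. This matches the rule already used in the multiple imputation of HiSCR.
2. Delete *only*, and pre-specify for endpoint 4 a sensitivity analysis by CMH in all ITT subjects with NRI. Subjects whose HS improved enough to make surgery unnecessary remain successes.
3. Add one sentence giving the reason for using observed cases as the primary analysis. Whether NRI should replace it is for the sponsor to judge.

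The cost is a few words in the SAP before unblinding and one extra table. Success proportions become slightly lower. The NRI table will count leavers for reasons unrelated to HS as failures, so it can itself mislead when such dropout is unequal (about 7.5% rejection in C). It should be read beside the primary analysis, not in place of it.
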